11.1.4 Reporting of AEs and SAEs

All AEs must be recorded in the case report form, defining relationship to IMP and severity. The frequency of each AE should always be recorded to indicate if the event is intermittent, continuous, one time event etc. If the same AE occurs repeatedly at approximately the same strength in the same patient this AE should be counted only once. If any aspect of the AE changes (including but not limited to severity, frequency, causality) a new AE should be recorded. AE start and end dates should be clearly defined in the CRF.

As soon as the Investigator is aware of a potential SAE, he/she should contact the Pharmacovigilance (PV) CRO monitor by phone, fax or e-mail, and in any case no later than 24 hours after the knowledge of such a case. The contact information, is provided in the Investigator Site File.

At the time of the call, the Investigator must provide as a minimum requirement, the Patient number, birth date, nature of the SAE, and a preliminary assessment of causality. The Investigator should follow-up the initial notification of the potential SAE by faxing a copy of the SAE reporting form to PV CRO at the number provided in the Investigator Site File. The faxed SAE reporting form should be received to the PV CRO within 24 hours after knowledge of such a case.

Follow-up information on an existing SAE that is fatal or life-threatening should be reported by the Investigator to PV CRO within 5 days after the initial report. Where appropriate, hospitalisation or autopsy reports should be made available. All SAEs will be followed up until resolution (i.e., asymptomatic, stabilisation or death).

AE's should be reported for the entire study duration up to and including the follow up period. Following completion of the study, if the Investigator becomes aware of any AE that is potentially related to the IMP the Sponsor should be notified.

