The proportion of moderate patients achieving an IGA of 0 (clear) or 1 (almost clear) and a decrease in 2 point in IGA score was significantly greater in the DS107 capsules group (8/29 patients, 28%) compared to placebo group (6/38 patients, 16%) in patients with moderate AD at baseline ($p = 0.036$). Similar efficacy trends were observed in the severe/very severe population where 3 out of 22 patients (13%) treated with DS107 capsules met the Responder criteria compared to 0 out of 13 patients in the Placebo group. Statistical significance could not be achieved due to the low number of patients in each group and lack of primary response in placebo.

The effect of DS107 capsules was consistently higher than placebo for all of the efficacy endpoints evaluated in this study, both investigator scores and patient scores. Pruritus is the most important symptom for patients suffering from AD. It has a significant impact on sleep and quality of life (Hong et al., 2011). Pruritus sensation was significantly decreased from Baseline at Week 4 in patients receiving DS107 compared to patients receiving Placebo. This difference in pruritus was both statistically and clinically significant as shown by a decrease in pruritus of 39.5% for patients randomized to DS107 and of only 10.05% in patients randomized to placebo at week 4.

No deaths or SAEs were observed throughout the course of this study. There were no drug related AE's associated with safety lab results, physical exams or vital signs. AEs were mild to moderate and transient. The most common AEs observed in the DS107 group were gastrointestinal in nature. Overall

the tolerance of DS107 capsules administered over 8 weeks was acceptable in comparison with Placebo and DS107 appears safe and well tolerated.

Topical DS107

Three studies have been completed with DS107 Cream.

A Phase 1 clinical study (DS107E-01) was carried out to investigate the safety and tolerability of topically administered DS107 cream in human volunteers at five dose levels (0.1%, 0.5%, 1%, 2.5% and 5%) applied twice daily for 14 days (with a matched placebo cream).

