Secondary Endpoint(s)	
 • Proportion of patients achieving an IGA score of 0 (clear) or 1 (almost clear) and a decrease of at least 2 points in IGA in treated population compared to placebo population from baseline to Week 2, 4, 6 and 10. • Proportion of patients achieving a decrease of at least 2 points in IGA in treated population compared to placebo population from baseline to Week 2, 4, 6, 8 and 10. • Change from baseline in Eczema Area and Severity Index (EASI) in treated population compared to placebo population at Weeks 2, 4, 6, 8 and 10. • Change from baseline in Numeric Rating Scale (NRS) for Pruritus in treated population compared to placebo population at Weeks 2, 4, 6, 8 and 10.
Exploratory Endpoints	
 • Time to response by Week 8. • Probability of being in response (PBIR) between Weeks 2 and 8. • Sustained efficacy between Weeks 8 and 10. • Change from baseline in the Dermatology Life Quality Index (DLQI) score in treated population compared to placebo population at Week 2, 4, 6, 8 and 10 and from Week 8 to Week 10.

	
 • Change from baseline in the Patient Orientated Eczema Measure (POEM) score in treated population compared to placebo population at Week 2, 4, 6, 8 and 10 and from Week 8 to Week 10. • Change from baseline in the Patient Global Impression of Severity (PGI-S) score in treated population compared to placebo population at Week 2, 4, 6, 8 and 10 and from Week 8 to Week 10. • Change from baseline in the Patient Global Impression of Change (PGI-C) score in treated population compared to placebo population at Week 2, 4, 6, 8 and 10 and from Week 8 to Week 10. • Plasma DGLA concentrations in treated population compared to placebo population at Baseline/Day 0, Week4, Week 8 and Week 10 (samples to be retained for the potential analysis at a later date). • Determination of AD biomarkers in treated population compared to placebo population at Baseline/Day 0 and Week 8/Early Termination (samples to be retained for the potential analysis at a later date).
Safety Endpoints	
 • Adverse event (AE) and serious adverse event (SAE) frequency and severity. • Safety laboratory parameters (haematology, clinical chemistry). • Clinical safety examinations (vital signs, physical examination).

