2.2.13.3 Adverse Events

Counts and percentages of subjects who experienced any of the following will be presented by treatment group, as well as a total DS107 treatment group that includes both the 1g and 2g DS107 subjects: any AE, any IMP related AE, any AE requiring modification of study medication dosing (dose reduced, drug interrupted), discontinuations of study participation due to an AE (drug withdrawn), any serious adverse events (SAE), deaths, or IMP related SAEs. Only those adverse events determined to be treatment emergent (TEAE) will be presented (where Qlabel="Treatment

Emergent” from the SUPPAE SDTM dataset). Treatment emergent adverse events are those events with the date of AE onset being greater than or equal to the date of the first dose date of study drug. A two-sided Fisher Exact test will be utilized for an overall global test and for the pair-wise comparisons of each treatment compared to placebo.

Verbatim terms on the case report forms will be coded to preferred term (PT) and related system organ class (SOC) using MedDRA Coding Dictionary Version 19.1. The number and percentage of subjects who experience treatment-emergent adverse events (TEAE) will be tabulated by System Organ Class (SOC) and Preferred Term (PT) within each treatment group. The number of events will be tabulated by System Organ Class (SOC) and Preferred Term (PT) within each treatment group. In addition, a tabulation of adverse events that occur at a frequency of 2% or greater at the SOC or PT level will be prepared. A two-sided Fisher Exact test will be performed on system organ class (SOC) with a 2% or greater frequency to facilitate evaluation of potential safety differences among treatments.

Adverse events will be counted only once for a subject within each Preferred Term and System Organ Class; thus, since a subject may have more than one Preferred Term within an SOC, percentages of PT may not sum to the percentage in the SOC. If a subject reports a Preferred Term multiple times with differing severities (mild, moderate or severe), only the most severe is counted but all events will be counted. If a subject reports a Preferred Term multiple times with differing relationships to IMP, only the one that is related to IMP is counted.

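### The planned adverse-event counts by arm count AE records, not occurrences, because same-strength repeats are merged and any change opens a new AE (minor)

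*Protocol*

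**What the plan says.** Protocol Section 11.1.4 gives sites three instructions that bear on this point.

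- Pattern: "The frequency of each AE should always be recorded to indicate if the event is intermittent, continuous, one time event etc".
- Repeats: "If the same AE occurs repeatedly at approximately the same strength in the same patient this AE should be counted only once".
- Changes: "If any aspect of the AE changes (including but not limited to severity, frequency, causality) a new AE should be recorded".

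The same paragraph asks for clear start and end dates.

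SAP Section 2.2.13.3 plans two kinds of table. The subject-level one counts each person once: "Adverse events will be counted only once for a subject within each Preferred Term and System Organ Class". The event-level one does not: "The number of events will be tabulated by System Organ Class (SOC) and Preferred Term (PT) within each treatment group". Where a subject reports a preferred term several times at differing severities, the SAP says "only the most severe is counted but all events will be counted". Where the reports differ in relationship to study drug, the related one is counted.

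The safety endpoint that these tables serve, in the SAP's protocol summary, is "Adverse event (AE) and serious adverse event (SAE) frequency and severity".

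**The concern.** A table of event numbers by arm invites the reader to compare how often events happened. Under Section 11.1.4 the unit in that table is not an occurrence. Several separate episodes of similar strength become one AE, while one continuous episode becomes several AEs if its severity, pattern or attribution is revised. Nothing in the SAP undoes either step.

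Tolerability is where this could matter. On the Phase 2a study, Protocol Section 1.6 reports: "The most common AEs observed in the DS107 group were gastrointestinal in nature". It describes the gastrointestinal events in Phase 1 as fairly short and self-resolving. Whether such events recur under daily dosing is not stated. If they do, and at similar intensity, their number is the information that the recording rule discards. Two arms with equal numbers of affected patients but different recurrence would then show the same event count.

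**Working it through.** The plan gives no figure to reproduce. The check applies the two recording rules to assumed histories, because the documents contain no episode data.

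**Inputs.** The merging and splitting rules come from Protocol 11.1.4. The rule that every record enters the event count comes from SAP 2.2.13.3. Assumed: 20 affected patients in each arm, and placebo patients with one unchanging episode each.

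**Formula.** Put a patient's states for one preferred term in time order, across episodes. Records = 1 + number of changes between successive states. True episodes = number of separate onsets.

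**Single patients.**
- Six identical mild episodes: 6 true; records = 1 + 0 = 1.
- One episode rated mild, then moderate, then mild: 1 true; records = 1 + 2 = 3.

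**Arms (active v placebo).**

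| History of each affected active patient | True episodes | Records counted as events |
|---|---|---|
| 2 identical episodes | 20 × 2 = 40 v 20 | 20 × 1 = 20 v 20 |
| 3 identical episodes | 20 × 3 = 60 v 20 | 20 × 1 = 20 v 20 |
| 6 identical episodes | 20 × 6 = 120 v 20 | 20 × 1 = 20 v 20 |
| 1 episode, 2 states | 20 × 1 = 20 v 20 | 20 × 2 = 40 v 20 |
| 1 episode, 3 states | 20 × 1 = 20 v 20 | 20 × 3 = 60 v 20 |

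The number of affected subjects is 20 v 20 in every row, so with the planned 100 per arm the incidence stays at 20/100 = 20% in both arms.

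**Second reading of the rule.** Frequency is one of the aspects whose change opens a new AE. A first episode labelled one-time that later becomes intermittent could then give 1 + 1 = 2 records, however many repeats follow. The first three rows would all show 20 × 2 = 40 v 20, against true counts of 40, 60 and 120 v 20. The count still does not follow recurrence beyond the second episode.

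**Can the SAP recover the episodes?** The pattern label says that an AE was intermittent, not how many times it occurred. A single record covering several episodes has only one start and one end date. The number of merged episodes is therefore lost at entry. Split records are different: with dates on each, contiguous records can be rejoined. Doing so returns the last two rows to 20 v 20 and leaves the first three at 20 v 20.

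**The case against.** The strongest reply is that little depends on these counts. The SAP leads with subjects, counts each once per term, and takes the worst severity and the related report where reports differ. Fisher exact tests are described for the subject-level overview and for organ classes at 2% or more; no test or rate model uses event numbers. The serious-event table in SAP 2.2.13.3.1 also counts subjects. All of this stands and sets the size of the point.

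A reader might infer that recurrences disappear from the data. They do not: the pattern label keeps the fact of recurrence, and only the number is lost.

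A reader might also infer that the count runs opposite to burden. The documents do not support that. A worsening or a change of pattern adds records and may be real burden, so the error can go either way. An excess such as 40 v 20 arises in the example only because active-arm episodes change state more often, which is itself a difference between arms.

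It could be said that *counted* is an analysis rule rather than an entry rule. But it stands among the investigator's recording instructions, and read as an analysis rule it would sit badly with the SAP's statement that all events are counted.

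Finally, the SAP sentence on differing relationship does not repeat that statement. A record opened only for a causality change might therefore be left out of the event count; the text does not settle this. The severity examples above do not depend on it.

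**Conclusion.** The point holds as a minor one. The descriptive event counts by arm do not measure how often AEs occurred. They can hide a difference in recurrence (120 v 20 shown as 20 v 20 in the example) or show one where episodes are equal in number (20 v 20 shown as 60 v 20). The sizes are illustrative; the real effect depends on how often events recur or are re-rated, which the documents do not say.

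This assumes that sites follow Section 11.1.4 as written and that each AE record enters the table as one event.

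It would be wrong to conclude that the AE frequency endpoint goes unreported or that the safety comparison fails. Subject-level incidence, worst severity, relatedness and every planned Fisher test are unaffected. Nor do the documents say that the gastrointestinal events recur; that is a reason for care in labelling, not evidence of a missed signal.

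**What to change.** 1. **SAP 2.2.13.3.** Before counting events, merge records of the same subject and preferred term that are contiguous in time, or that share an episode identifier if one is collected. Keep the worst severity and any related rating, which agrees with the SAP's existing subject-level rules.
2. **Protocol 11.1.4.** Treat a change of causality alone as an update to the existing AE, not as a new AE.
3. **Presentation.** Show event counts alongside the intermittent, continuous or one-time label, with a note that they do not measure recurrence. Alternatively, drop the event-count tables and report subjects only.

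The cost is a small amount of programming and one sentence of protocol wording. Entering every recurrence as its own AE is not needed for this fix; it is a debatable convention and would add entry work at sites.

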11.2 Serious Adverse Reactions and Unexpected Adverse Reactions

11.2.1 Definitions

Adverse Reaction:

All noxious and unintended responses to a medicinal product related to any dose should be considered adverse drug reactions.

The phrase "responses to a medicinal product" means that a causal relationship between a medicinal product and an adverse event is at least a reasonable possibility i.e. the relationship cannot be ruled out.

For marketed medicinal products, an adverse reaction is a response to a drug which is noxious and unintended and which occurs at doses normally used in man for prophylaxis, diagnosis, or therapy of disease or for modification of physiological function.

Unexpected Adverse Reaction:

An adverse reaction, the nature or severity of which is not consistent with the applicable product information (e.g. Investigator's Brochure for an unauthorised investigational product or similar product information sheet such as the Summary of Products Characteristics (SPC)).

Suspected Unexpected Serious Adverse Reaction (SUSAR):

Any serious adverse reaction that might be related to the IMP and are unexpected according to the definition above.

11.2.2 Reporting of suspected unexpected serious adverse reactions

Suspected unexpected serious adverse reactions (SUSARs) will be reported by PV CRO according to appropriate Competent Authority and Ethics Committee requirements. SUSARs will be reported to Investigators according to ICH Good Clinical Practice and to local regulations. SUSAR reporting to the Competent Authorities and Ethics Committees will be performed according to local regulations in an unblinded manner. The Competent Authorities will be notified of all SUSARs through the Eudravigilance database.

Fatal and life-threatening SUSARs should be reported by PV CRO as soon as possible to the Competent Authorities and Ethics Committees according to local regulations, and in any case no later than seven calendar days, after knowledge by PV CRO of such a case. Relevant follow-up information on the case will be subsequently communicated within an additional eight days. All other SUSARs shall be reported to the Competent Authorities concerned and to the Ethics Committee concerned according to local regulations as soon as possible but within a maximum of fifteen days of first knowledge by PV CRO.

11.3 Differentiation of Treatment Failure and AE

Please note, that the lack of improvement of the symptoms of AD is not an AE and should be reported as treatment failure.

11.4 Pregnancy Reporting

If a patient or a patient's partner becomes pregnant during the study, the patient should inform the study site as soon as possible. Upon confirmation of the pregnancy, the patient must be withdrawn from study drug but may continue study participation. The Investigator must complete a study-specific Pregnancy Form upon confirmation of a pregnancy and send it to the Sponsor within 24 hours of confirmation of the pregnancy.

Post-treatment follow-up should be done to ensure patient safety. Pregnancy is not itself an AE or SAE, however maternal/foetal complications or abnormalities will be recorded as AEs or SAEs as appropriate. The investigator will follow the pregnancy until completion (or until pregnancy termination) and notify the Sponsor of the outcome as a follow up to the initial Pregnancy Form.

12 STATISTICAL METHODOLOGY AND DATA MANAGEMENT

12.1 Study Design

This clinical trial employs a randomized, double-blind, placebo-controlled parallel group design. Randomisation is used to minimise assignment bias and to increase the likelihood that known and unknown patient attributes (e.g. demographic characteristics) are evenly balanced across the treatment groups. Blinding is used to reduce potential bias during data collection and evaluation of safety and efficacy. The use of placebo as comparator is justified as a reasonable design to assess safety and efficacy in patients based on the brevity of the study duration and the absence of any possible long-term irreversible damage that may be the result of placebo treatment. A full description of the study design is presented in Section 6 above.

12.2 Randomisation

At least 300 patients will be randomized into double-blind treatment groups in a 1:1:1 ratio by an IWRS.

- Treatment group A: 1g DS107 (2 DS107 capsules and 2 placebo capsules) administered once-daily for 8 weeks
- Treatment group B: 2g DS107 (4 DS107 capsules) administered once-daily for 8 weeks
- Treatment group C: Placebo (4 placebo capsules) orally administered once-daily for 8 weeks

A randomization list permuted blocks and stratified by site will be generated by the Sponsor or its designee. The randomization schedule with study drug assignments will be generated prior to the start of the study and will be known only to the individuals responsible for labelling the study drug, the statisticians generating the schedule and the IWRS team responsible for implementing the schedule. The IWRS will assign a medication kit number to each patient and the contents will be based on the randomization code.

At the investigational site, each patient will be assigned a patient identifier number during screening that will be used on all patient documentation. The patient identifier number will contain the site number and the patient number assigned in numerical order at the screening visit (e.g.: 102-10 for the tenth patient screened at the site number 02). Patient numbers will be assigned in ascending order starting with 01.

The treatment assignment procedure will use blocks of sufficient size to maintain a blind and balance across treatment arms. Following successful completion of the screening/baseline evaluations and confirmation that the patient is eligible for participation, the patient will be randomised to treatment. This will be performed by the Investigator using the IWRS which will assign a medication number to the patient.

12.3 Estimation of Sample Size

In the Phase 2a trial, IGA response rates of 21.6% and 11.8% were observed for DS107 and Placebo respectively. Assuming these rates and a significance of 5%, 300 evaluable patients (100 patients per treatment arm) will yield 45% power for comparisons between the active doses and placebo in this study.

12.4 Blinding and Code Breaking Instructions

All study site personnel, as well as the personnel involved in the monitoring or conduct of the study, will be blinded to the individual patient treatment assignments. Randomisation details will be kept strictly confidential, accessible only in an emergency to authorized persons, until the time of formal unblinding. The blinded code for the trial will be broken only after all patient data has been recorded and verified and the database locked.

Emergency unblinding will be carried out through the IWRS system with relevant site personnel and pharmacovigilance monitors provided with the required system access to carry out unblinding.

12.5 Interim Analysis

An interim analysis will be conducted once 50% of planned patients have completed their Week 8 assessments. This will be conducted in accordance with sponsor SOP “Interim Analysis of Clinical Studies”.

12.6 Data Analysis

Data analysis will be performed at the CRO. All computations will be completed using SAS® version 9.1.3 or later. Graphical summaries will be produced using SAS®. A detailed description of the analyses to be performed will be provided in the statistical analysis plan (SAP).

Continuous variables will be summarized in tables and will include the number of patients, mean, standard deviation, median, minimum, and maximum. Categorical variables will be presented in tables as frequencies and percentages.

